9.1 Screening Examination

The screening examination will take place between Day -42 and randomization. An informed consent must be signed by the subject before any screening procedure takes place. Subject data to be collected at the Screening Examination includes:

- Informed Consent
- Eligibility Criteria
- Medical History
- Physical Exam
- Height, Weight, BMI
- Vital Signs
- Performance Status (ECOG)
- Concomitant Medications
- Adverse Events
- CBC with Platelets (hemoglobin, hematocrit, platelet count, white blood cell count, total [absolute] neutrophils)
- Serum Chemistry (sodium, potassium, chloride, total CO₂ [bicarbonate], calcium, BUN, creatinine, glucose, albumin, total bilirubin, total protein, alkaline phosphatase, AST, ALT)
- Testosterone
- PSA
- CT or MRI of the abdomen and pelvis and bone scans should be performed to document that there is no definite evidence of metastatic disease at the time of screening.
 - These scans must occur within 84 days prior to enrollment (Day 1).

9.2 Subject Registration

After signing informed consent and completing eligibility screening, subjects who are selected to participate will be registered with the lead site (Duke) and with their study site/institution. A record of subjects who fail to meet entry criteria (i.e., screen failures) will be maintained. Subject registration must be complete before beginning any treatment.

9.2.1 Informed Consent

Authorized study personnel should fully explain the scope of the study to each subject before obtaining informed consent. Subjects should be advised of any known risks inherent in the planned procedures, of any alternative treatment options, of their right to withdraw from the study at any time for any reason, and of their right to privacy.

When obtaining informed consent, study personnel should:

First: Confirm that the subject is a potential candidate for study participation.

Next: Obtain dated and signed informed consent.

Finally: Confirm that the subject is eligible as defined in **Section 8** (Inclusion/Exclusion Criteria). A record of subjects who fail to meet entry criteria (i.e., screening failures) will be maintained.

For subjects consented at the lead site ONLY, registration in the Duke clinical trial subject registry must be completed within 1 business day of the subject providing informed consent.

9.2.2 Lead Site Registration

Subject registration for all subjects signing informed consent will be completed by Duke University Medical Center Genitourinary Oncology Group. Following consent and completion of the Eligibility Checklist, documents will be submitted for review and registration of subject. Enrolled subjects will be assigned a unique study ID.

Refer to Subject Registration Instructions for details.

Subjects will be enrolled only after all pre-treatment screening evaluations are completed and all eligibility criteria are met. Once the subject has signed consent and been found to meet all eligibility criteria, the subject will be enrolled, and a unique patient study identification number will be assigned. Treatment must not commence until the subject has received his identification number from the lead site.

9.2.3 Institutional Registration

Subject registration at each study site/institution will be conducted according to the institution's established policies. Prior to registration, subjects will be asked to sign and date an Institutional Review Board (IRB)-approved consent form. Subjects must be registered with their local site/institution and with the lead site before beginning any treatment or study activities.

9.3 Baseline Exercise Testing

Baseline exercise testing will take place up to 30 days prior to randomization, over approximately 2 days. An informed consent must be signed by the subject before any screening procedure takes place. Subject data to be collected at Baseline Exercise Testing includes:

- CPET
- Chair Stand
- Timed Up and Go
- 6 Minute Walk Distance (**Duke patients only**)
- Muscular Strength (*must be at least 24 hours before or after CPET to allow for adequate recovery*)
- Muscle CSA (MRI, **protocol v1-v15 only**)
- Muscular Endurance (*must be at least 24 hours before or after CPET to allow for adequate recovery*)
- Body Composition
- FACT-P
- FACIT-Fatigue
- Godin Leisure Time Exercise Questionnaire
- Food Frequency Questionnaire
- Fasting glucose, insulin, HgbA1c (fasting, pre-exercise, **protocol v1-v15 only**)
- PSA
- Metabolomics (fasting, pre-exercise)

Of note, CPET and Muscular Strength/1-RM results will be used to formulate the exercise training prescription for Arm B.

9.4 Randomization

Subjects will be randomized after inclusion/exclusion criteria are met and after exercise testing (specifically, CPET) is complete. Randomization can be on Day 1 for Arm A and up to 14 days prior to start of exercise program (Day 1) for Arm B.

9.5 Lead-In Period

Subjects will be randomized to usual care or exercise training up to 14 days prior to Day 1, but only after eligibility is confirmed and baseline exercise testing (specifically, CPET) has been performed. See **Sections 6.1.4** and **9.4** for randomization details. See also **Schedule of Events**, above.

Arm A, ENZ – ADT plus Usual Care: Subjects randomized to usual care will be asked not to make any changes in their physical activity beginning on Day 1. These subjects will start ENZ – ADT on Day 29 (week 5) after the 4 week lead-in period. This delay is felt to be insignificant from a clinical perspective. While two Phase III studies are currently examining this question (NCT00439751; NCT00110162), the delay in initiation of ADT in these studies is much longer than 4 weeks. There is currently no evidence that a delay, especially one as short as 4 weeks, in starting ADT in men with non-metastatic prostate cancer, affects outcomes.⁸⁸

Arm B, ENZ – ADT plus Exercise Training: Subjects randomized to exercise training will begin the exercise training program detailed below beginning on Day 1. The goal for the ENZ-ADT plus exercise training will be 3 supervised exercise sessions per week at an intensity between 50 and 100% of the individually determined exercise capacity (at baseline) for aerobic training and an intensity between 60% and 80% of one-repetition maximum (1-RM) for resistance training for 30-90 minutes/session. The exercise training intervention is designed such that participants begin exercising at a low intensity (~50%-60% VO₂peak) that is subsequently increased to more moderate to vigorous intensity (~70%-80% VO₂peak) when appropriate. All interventions will be individually tailored to each subject following the principles of aerobic or resistance training prescription guidelines for adults as recommended by the American College of Sports Medicine (ACSM).⁸⁹ All exercise sessions will also be performed in a supervised setting with one-on-one supervision by certified exercise physiologists, physical therapists, exercise physiology students under the supervision of an ACSM-certified exercise physiologist, or trained designee. The exercise prescription for each subject will be created centrally by either [name] group at MSKCC or the CPX Lab at Duke based on both the interpretation of the CPET plus Muscular Strength/1-RM data and a standardized template, within 24-48 hours of these tests.

The major reason for early training during this Lead-In Period is to 'buffer' the expected rapid deleterious impact of hormonal therapy on cardiovascular and skeletal muscle function. This 'pre-treatment' exercise training is hypothesized to attenuate this impact that, in turn, will facilitate higher intensity exercise training during hormonal therapy.

9.6 Treatment Period 1: ENZ-ADT plus either Usual Care or Exercise Training

Arm A, ENZ – ADT plus Usual Care: Beginning on Day 29 (week 5), subjects will be treated with androgen deprivation therapy (ADT) per standard of care (orchiectomy, GnRH agonist, or GnRH antagonist to maintain total testosterone <50 ng/dl for the remaining 32 weeks of the study). In addition, subjects will take enzalutamide (ENZ) 160 mg by mouth daily for the remaining 32 weeks of the study. The dosing of both the GnRH agonist and enzalutamide (160 mg daily) is the standard-of-care dosing. The treatment duration of approximately 8 months was selected to achieve maximal efficacy while minimizing toxicity and is based on intermittent hormonal therapy regimens studied in Phase III clinical trials.^{22,23} Concomitant medication will be evaluated at every clinic visit during enzalutamide therapy. Concomitant medications include all vitamins, herbal remedies, over the counter, and prescription medications.

Arm B, ENZ – ADT plus Exercise Training: Beginning on Day 29 (week 5), Subjects randomly allocated to this group will receive the same ADT-ENZ regimen as described above. In addition, subjects will continue the defined exercise training initiated during the Lead-In Period for a total of 16 weeks (through Day 113, week 17).

The window is ± 7 days for this period, EXCEPT Day 29 (week 5) which has a window of ± 3 days. See **Schedule of Events**, above.

Subject data to be collected during Treatment Period 1 includes:

- Physical Exam
- Height, Weight, BMI
- Vital Signs
- Performance Status (ECOG)
- Concomitant Medications
- Adverse Events
- CBC with Platelets (hemoglobin, hematocrit, platelet count, white blood cell count, total [absolute] neutrophils)
- Serum Chemistry (sodium, potassium, chloride, total CO₂ [bicarbonate], calcium, BUN, creatinine, glucose, albumin, total bilirubin, total protein, alkaline phosphatase, AST, ALT)
- Testosterone (Day 57 and 113)
- PSA
- CPET (Day 29 and Day 113)
- Chair Stand (Day 113)
- Timed Up and Go (Day 113)
- 6 Minute Walk Distance (Day 113; **Duke patients only**)
- Muscular Strength (*at least 24 hours before or after CPET on Week 4, Week 10 (not in conjunction with CPET) and week 17 in treatment period 2*)
- Muscle CSA (MRI; Day 113; **protocol v1-v15 only**)
- Muscular Endurance (*must be at least 24 hours before or after CPET to allow for adequate recovery on week 4, week 10 (not in conjunction with CPET) and week 17 in treatment period 2*)
- FACT-P (Day 113)
- FACIT-Fatigue (Day 113)
- Godin Leisure Time Exercise Questionnaire (Day 113)
- Food Frequency Questionnaire (Day 113)
 - Fasting glucose, insulin, HgbA1c (Day 113; pre-exercise; **protocol v1-v15 only**)
 - Note that the glucose from the serum chemistry, if drawn in a fasted state, may be used.
- Body Composition (Day 113)
- Metabolomics (Day 57 and 113; fasting, pre-exercise)
- Collect Pill Diary for Enzalutamide

9.7 Treatment Period 2: ENZ-ADT

Subjects on both arms will continue ADT per standard of care and enzalutamide through Week 37 (Day 252).

The window is -7/+30 days for this period. See **Schedule of Events**, above.

Subject data to be collected during Treatment Period 2 includes:

- Physical Exam
- Height, Weight, BMI
- Vital Signs
- Performance Status (ECOG)
- Concomitant Medications
- Adverse Events
- CBC with Platelets (hemoglobin, hematocrit, platelet count, white blood cell count, total [absolute] neutrophils)
- Serum Chemistry (sodium, potassium, chloride, total CO₂ [bicarbonate], calcium, BUN, creatinine, glucose, albumin, total bilirubin, total protein, alkaline phosphatase, AST, ALT)
- Testosterone (Day 169 and 252)

- PSA
- FACT-P (Day 252)
- FACIT-Fatigue (Day 252)
- Godin Leisure Time Exercise Questionnaire (Day 252)
- Collect Pill Diary for Enzalutamide

9.8 End of Treatment and Safety Follow-Up

The End of Treatment/Safety Follow-Up visit will be on Day 252 (-7/+30 days). See Section **9.7** and the **Schedule of Events**, above.

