9 SCREENING, REGISTRATION, AND ON-STUDY TESTS AND PROCEDURES

In addition to assessment for the **primary** endpoint (VO₂peak) by cardiopulmonary exercise testing (CPET), **secondary** and **exploratory** assessments for functional capacity, quantitative skeletal muscle function, metabolic, patient-reported outcomes, PSA, and metabolomics endpoints will occur throughout the study as specified below in the Schedule of Events.

The important time periods during the study include:

- **Screening** on Day -42 to randomization
- **Exercise Testing on Day -30 to randomization**
- **Randomization on Day -14 to Day 1, but after exercise testing (specifically, CPET) is complete**
- **Lead-In** of Usual Care (UC) or Exercise Training starting on Day 1
- **Treatment Period 1:** Enzalutamide + ADT with either UC or Exercise Training from Day 29 to 113
- **Treatment Period 2:** Enzalutamide + ADT from Day 114 to 252
- **End of treatment/Safety Follow-Up** within 30 days after the last dose of enzalutamide or prior to initiation of cytotoxic or investigation therapy, whichever occurs first

All subjects will receive treatment with ADT + enzalutamide for 32 weeks.

In addition, subjects randomized to Exercise Training (Arm B) will undergo a 16 week combined aerobic and resistance exercise training program, including a 4 week Lead-In before starting therapy with ADT + enzalutamide and during the first 12 weeks of therapy with ADT + enzalutamide.

SCHEDULE OF EVENTS

Phase		Screen	Baseline Exercise Testing ^{c,p}	4 Week Lead-In ^p		Treatment Period 1: Enzalutamide + ADT +/- Exercise Training				Treatment Period 2: Enzalutamide + ADT and Safety Follow-up	Unscheduled Visit ^a
				2	3	4					
Clinic Visit Number		1				2	3	4	5 (EOT) SEE NOTE		
Day		-42 to randomization	-30 to randomization	1 ^q	22	29	57	64	113	252	
Week		-6 to -1		1	4	5	9	10	17 ^a	37 ^a	
Window (Days)		NA		NA	+6	±3	±7	±3	±7	-7, +30	NA
General Evaluations	See Section										
Informed Consent ^b	9.2.1	X									
Eligibility Criteria	8	X									
Medical History	9.12.1	X									
Randomization ^c	6.1.4			X ^c							
Physical Exam ^d	9.12.2	X				X	X		X	X	X
Height, Weight, BMI	9.12.2	X				X	X		X	X	X
Vital Signs ^e	9.12.2	X				X	X		X	X	X
Performance Status (ECOG) ^f	App. A	X				X	X		X	X	X
Concomitant Medications	6.1.3	X				X	X		X	X	X
Adverse Events ^g	10	X				X	X		X	X	X
Laboratory Evaluations											
CBC with platelets ⁱ	9.1-9.7	X ⁱ				X	X		X	X	X ^h
Serum Chemistry ⁱ	9.1-9.7	X ⁱ				X	X		X	X	X ^h

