9.9 Safety Follow-up Period

The Safety Follow-Up visit will be within 30 days after the last dose of enzalutamide or prior to initiation of cytotoxic or investigational therapy, whichever occurs first. See **Schedule of Events**, above.

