9.10 Off Study and End of Study

A subject is considered *off study* when he has completed the Safety Follow-Up visit. All subjects discontinuing study drug for any reason will have a Safety Follow-Up visit approximately 30 days after their last dose of study drug or prior to initiation of cytotoxic or investigational therapy, whichever occurs first.

Reasonable effort should be made to contact any subject lost to follow-up during the course of the study in order to complete study-related assessments and retrieve any outstanding data and study drug. Following unsuccessful telephone contact, an effort to contact the subject by mail using a method that provides proof of receipt should be attempted. Such efforts should be documented in the source documents.

The *end of the study* will occur when the last subject enrolled has completed his Safety Follow-Up visit. A database lock will occur once the data has been cleaned to the specifications in the data quality plan. The database will then be frozen, and no further changes will be permitted.

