9.11.2 Follow-up Requirements for Early Withdrawal

The Premature Withdrawal visit will be the same as the Safety Follow-Up visit. As mentioned above, all subjects discontinuing study drug for any reason will have a Safety Follow-Up visit approximately 30 days after their last dose of study drug or prior to initiation of cytotoxic or investigational therapy, whichever occurs first.

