10.1 Adverse Events

An adverse event (AE) is any untoward medical occurrence in a subject undergoing a study procedure/intervention and/or receiving study drug; which may or may not have a causal relationship with study procedures, interventions or treatments. For this protocol, the definition of AE also includes worsening of any pre-existing medical condition. An AE can therefore be any unfavorable, unintended or worsening sign or symptom (including an abnormal laboratory finding, or disease temporally associated with exercise testing for both arm A and arm B; exercise training for arm B; and/ or related to the use of enzalutamide. Abnormal laboratory findings without clinical significance (based on the PI's judgment) should not be recorded as AEs. But laboratory value changes that require therapy or adjustment in prior therapy are considered adverse events.

Research exercise-related adverse events will be collected from the baseline exercise testing to the End of Study visit (as defined in **Section 9.8**) for all subjects (Except anticipated AEs-see section 10.1.2). All subjects will have enzalutamide related adverse events collected from the start of study drug on week 5, day 29 through the Safety Follow-up visit.

Serious adverse events that are related to study exercise procedures (CPET, 1RM, Chair testing, etc) are recorded from the time the informed consent form is signed until the Safety Follow-Up visit (withdrawal or screen failure). All SAEs will be collected regardless of attribution starting once the patient takes his first dose of study drug through the Safety Follow-Up visit. All AEs and SAEs must be recorded in the subject medical record and adverse events case report form.

AEs will be assessed according to the CTCAE version 4.0. If CTCAE grading does not exist for an AE, the severity of the AE will be graded as mild (1), moderate (2), severe (3), life-threatening (4), or fatal (5).

Attribution of AEs will be indicated as follows:

- Definite: The AE is clearly related to the study drug and/or exercise training and/or exercise testing
- Probably: The AE is likely related to the study drug and/or exercise training and/or exercise testing
- Possible: The AE may be related to the study drug and/or exercise training and/or exercise testing
- Unlikely: The AE is doubtfully related to the study drug and/or exercise training and/or exercise testing

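### Adverse event collection ends at a combined End of Treatment/Safety visit whose timing the protocol states inconsistently, so follow-up after the last dose can be anywhere from 0 to about 30 days

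*Combined protocol and SAP*

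**What the plan says.** Section 9.7 continues enzalutamide through Day 252 in both arms. The combined visit that follows is timed in three ways:

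- **Around Day 252.** Section 9.8: "The End of Treatment/Safety Follow-Up visit will be on Day 252 (-7/+30 days"). The Schedule of Events column for Day 252 carries the same window.
- **Up to 30 days after the last dose.** The period list at the start of Section 9 has "within 30 days after the last dose of enzalutamide or prior to initiation of cytotoxic or investigation therapy", whichever comes first. Section 9.9 also has "within 30 days after the last dose of enzalutamide".
- **About 30 days after the last dose.** The Schedule NOTE places the combined visit 30 days after the last dose. Section 9.10 has "approximately 30 days after their last dose of study drug", and 9.11.2 repeats that timing and adds "The Premature Withdrawal visit will be the same as the Safety Follow-Up visit".

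This visit closes safety collection. Section 10.1 states "All subjects will have enzalutamide related adverse events collected from the start of study drug on week 5, day 29 through the Safety Follow-up visit" and "All SAEs will be collected regardless of attribution starting once the patient takes his first dose of study drug through the Safety Follow-Up visit". Under 9.10 a man is off study "when he has completed the Safety Follow-Up visit".

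Footnote g of the Schedule sets a fixed 30-day collection period and a phone contact, but only for men who do not have the visit.

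FACT-P, FACIT-F and the Godin questionnaire are scheduled at the same visit (Schedule of Events; 9.7).

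**The concern.** The nominal visit day is also the planned last dosing day. A site that books Day 252 complies with 9.8 and 9.9, ends AE and SAE collection that day, and owes the man no further contact. A site that follows the NOTE books about Day 282 and collects for 30 more days. Footnote g sharpens the contrast, because the man who fails to attend is followed longer than the man who attends on time.

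Two planned outputs are affected. The AE rate in each arm is a secondary endpoint (Section 5) and is displayed by arm (12.5), so it would rest on unequal observation periods. Events soon after stopping, including SAEs, could go uncollected in some men without any deviation from 9.8, 9.9 or 10.1.

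The week 17 to week 36 comparison of patient-reported outcomes (12.5) is meant to show whether the exercise effect lasts. It would mix men still on enzalutamide with men up to about 30 days off it.

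**Working it through.** **Inputs.** Enzalutamide start Day 29, window ±3 days (9.6). Planned last dose Day 252 (9.7). Visit window Day 252 −7/+30 (9.8). Missed-visit rule of 30 days (footnote g). Mean terminal half-life 5.8 days, measured in men with castration-resistant disease (4.2.2). Sample size 40 (6.1).

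**Treatment duration, reproducing the plan's figure.** 252 − 29 + 1 = 224 days; 224 / 7 = 32 weeks, as stated.

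**Visit window under 9.8.** 252 − 7 = Day 245 to 252 + 30 = Day 282.

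**Post-dose follow-up = visit day − last-dose day, for a Day 252 last dose**

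| Rule followed | Post-dose days |
|---|---|
| 9.8 alone | −7 to +30 |
| 9.9 or Section 9 list | 0 to 30 |
| 9.8 and 9.9 together | 0 to 30 |
| NOTE, 9.10, 9.11.2 | about 30 |
| No visit held (footnote g) | 30 |

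Starting cytotoxic or investigational therapy can bring the visit forward under 9.9, the NOTE, 9.10 and 9.11.2.

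If 32 weeks are counted from a Day 26 start, the last dose is Day 249 and the 9.8 range is 245 − 249 = −4 to 282 − 249 = +33. From a Day 32 start, the last dose is Day 255 and the range is −10 to +27. The lower limit of 0 used here is therefore not the most extreme reading of 9.8.

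**Consistency of the two ends.** A Day 282 visit after a Day 252 last dose meets every statement. A Day 252 visit meets 9.8, 9.9 and the Section 9 list, but not the NOTE, 9.10 or 9.11.2.

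**Share of the safety period.** 0/224 = 0% at one end; 30/(224 + 30) = 30/254 = 11.8% at the other.

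**Person-days.** 40 × 0 = 0 to 40 × 30 = 1,200.

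**Drug remaining.** With simple exponential decline of the parent drug, the fraction left after d days is 0.5^(d/5.8). At d = 0 it is 100%. At d = 30 it is 0.5^5.17 = 2.8%. A Day 252 visit thus captures none of the washout, and a visit at 30 days captures nearly all of it. This covers the parent drug only; Section 4.2.2 gives no half-life for the active metabolite.

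**The case against.** The strongest reply is that 30 days is the evident intent. The NOTE, 9.10 and 9.11.2 all give it, 9.8 refers the reader to the Schedule that carries the NOTE, and the +30 in 9.8 ends exactly 30 days after a Day 252 last dose. On that reading footnote g simply gives absentees the same 30 days, and the 0-day case breaches three statements.

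This is right about intent, and it means some sites may already provide full follow-up. It does not settle the matter. No section says which timing governs, 9.8 and 9.9 still permit a visit on the last dosing day, and a visit at Day 282 puts the end-of-treatment questionnaires 30 days off enzalutamide, although Section 5 ties Day 252 to the end of the 32 weeks of treatment. One visit cannot serve both purposes.

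Other points stand:

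- The 1,200 person-days is a bound. The documents contain no data on actual visit timing.
- Both arms follow the same rules, and no mechanism for a difference between arms is apparent.
- Exercise ends on Day 113, so even a Day 252 visit gives 252 − 113 = 139 days of observation after training. The gap concerns late drug events, not exercise events.
- AE rates are only displayed by arm, and the late questionnaire comparison is descriptive.
- For any one man the two harms are alternatives: a visit at the last dose loses safety data, and a visit 30 days later takes the questionnaires off drug.

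**Conclusion.** The concern holds. The timing statements conflict in the current text, and AE and SAE collection hangs on the visit they define. Post-dose safety follow-up can range from 0 to about 30 days per man, which is 0% to 11.8% of a 254-day period and 0 to 1,200 person-days across the trial. These figures assume 40 men, a Day 252 last dose, and all men at one extreme or the other.

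The consequence is incomplete safety data that are not comparable between men, plus a late questionnaire assessment taken at varying times since the last dose. It does not touch the primary comparison of VO2peak at week 17, and it is not evidence of bias between arms. It merits correction because the remedy is cheap and already half-present in footnote g.

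**What to change.** 1. In Section 10.1 and footnote g, collect AEs and SAEs for every man through 30 days after the last enzalutamide dose, or until cytotoxic or investigational therapy starts if that is earlier. Use footnote g's phone contact whenever the visit falls before day 30.
2. In 9.10, make a man off study at the later of the visit and that contact.
3. Bring 9.8, 9.9, the Section 9 period list and the Schedule NOTE into line with this rule.
4. Keep the Day 252 visit for FACT-P, FACIT-F and Godin, and record days since last enzalutamide dose with each. Keep all men in the main comparison, and add an on-treatment-only analysis as a sensitivity check. This last analysis is desirable but secondary to items 1 to 3.

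**Cost.** Wording changes, submitted as an amendment with the IRB approval that 13.6 requires; one derived variable; one short additional analysis; and one phone call for each man seen before day 30, so at most 40 calls.
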